### 3 OBJECTIVES AND ENDPOINTS

Objectives & Endpoints:	Objectives	Endpoints
Primary	1. Phase 0: To measure the pharmacokinetic (PK) effects of infigratinib in recurrent high-grade glioma participants.	1. Phase 0: Total and Unbound infigratinib concentration in enhancing and non-enhancing tumor tissue (8hr), plasma (0-24H) and CSF (8hr) will be determined.
	2. Expansion Cohort: Examine progression-free survival in recurrent high-grade glioma participants with demonstrated PK effects	2. Expansion Cohort: 6-month Progression-free survival (PFS6) rate from time of surgery to date of recurrence
Secondary	1. Phase 0: PD Analysis	1. Phase 0: percentage of pERK+, MIB-1+ and Cleaved Caspase 3+ cells from the surgical tissue will be quantified and compared to baseline archival/biopsy tissue.
	2. Expansion cohort: To monitor safety and tolerability of study drug combinations in participants with recurrent high-grade glioma.	2. Expansion Cohort: Safety and tolerability: 
 
a. Drug-related toxicity
 
b. Number of Adverse Events through study completion, assessed up to 60 months
 
c. Treatment-emergent adverse events (TEAEs)
 
d. Deaths
 
e. Clinical laboratory abnormalities per CTCAE (Version 5.0)
 

Exploratory	1. Phase 0: Describe systemic PK	1. Phase 0: Systemic plasma PK profile parameters ( $T_{max}$ , $C_{max}$ , $t_{1/2}$ , $AUC_{0-24h}$ ) for total and unbound levels will be determined for infigratinib.
	2. Expansion cohort: Examine Overall Survival (OS) in recurrent high-grade glioma participants with demonstrated PK effects	2. Median Overall Survival (OS) from time of surgery to date of death from any cause

## 4 STUDY DESIGN

### 4.1 OVERALL DESIGN

This trial is an open-label, multicenter, Phase 0 trial that will enroll up to 20 participants with recurrent high-grade glioma (HGG) with FGFR1 K656E or FGFR3 K650E mutation or FGFR3-TACC3 translocation which are schedule for resection. In the lead-in cohort, a total of 20 HGG participants will be enrolled into the proposed phase 0 clinical trial. Participants will be administered infigratinib prior to surgical resection of their tumor.

#### 4.1.1 PHASE 0 DESIGN

The Phase 0 study will include treatment of recurrent high-grade glioma participants with 125 mg of infigratinib days 1- 7 prior to surgical resection. On Day 7, participants will receive infigratinib dose 7 to 9 hours prior to craniotomy for tumor resection.

To assess the PK endpoints listed above, blood, CSF and brain tumor tissue will be collected intraoperatively (enhancing and non-enhancing tumor tissue will be collected and analyzed separately). Additionally, blood samples will be obtained on Day 7 at pre-dosing (trough level), 0.5, 1, 2, 4, 6, 8, and 24 hours post dose. (Note: 24 h sample is the blood sample on Day 8).

A positive PK response in Phase 0 will be unbound concentrations of infigratinib reaching 5-fold higher than their respective cell-free biochemical IC50 values within the non-enhancing region of the tumor.

Phase 0 participants who do not proceed to the Expansion Cohort will be contacted every 3 months by letter or phone for collection of survival data.

#### 4.1.2 EXPANSION COHORT DESIGN

Participants with tumors demonstrating PK-response in Phase 0 will continue treatment with the same dose continuously for 21 days in 28d cycles after surgery. This will constitute the Expansion Cohort component of the study. PD biomarkers will be included for exploratory analyses. Expansion Cohort participants will be contacted every 3 months by letter or phone for collection of survival data.

Participants will be treated until unacceptable toxicity is observed, or until disease progression as assessed by RANO criteria.

### 4.2 SCIENTIFIC RATIONALE FOR STUDY DESIGN

The applicability of a Phase 0 study is most ideal in the situation of a targeted molecule, where there is availability of a validated biomarker for a well-understood target and evidence for linear drug kinetics. The Phase 0 trial will examine a novel therapy, infigratinib, in FGFR altered glioma patients which meets both these criteria.

### 4.3 JUSTIFICATION FOR DOSE

#### 4.3.1 DOSE RATIONALE FOR INFIGRATINIB

#### 4.1 END OF STUDY DEFINITION

A participant is considered to have completed the study if he or she has completed Phase 0 of the study including the Phone Follow Up visit shown in the Schedule of Activities (SoA), Section 1.2. All participants will be followed for survival. Participants will be followed until death for up to 5 years following the last dose administration.

The end of the study is defined as completion of the last visit or procedure shown in the SoA in the trial by the last participant enrolled across all sites.

## 5 STUDY POPULATION

### 5.1 INCLUSION CRITERIA

In order to be eligible to participate in this study, an individual must meet all of the following criteria:

1. Prior resection of histologically diagnosed high-grade gliomas (III and IV) defined as participants who have progressed on or following standard (Stupp regimen) therapy, which included maximal surgical resection, temozolamide, and fractionated radiotherapy.
2. Recurrence must be confirmed by diagnostic biopsy with local pathology review or contrast-enhanced MRI.
3. Have measurable disease preoperatively, defined as at least 1 contrast-enhancing lesion, with 2 perpendicular measurements of at least 1 cm, as per RANO criteria.
4. Sufficient archival/biopsy tissue available to confirm eligibility.
5. Archival or biopsy tissue must demonstrate: FGFR1 K656E or FGFR3 K650E mutation or FGFR3-TACC3 translocation from NGS sequencing or IHC and RT-PCR.
6. Ability to understand and the willingness to sign a written informed consent document (personally or by the legally authorized representative, if applicable).
7. Has voluntarily agreed to participate by giving written informed consent (personally or via legally authorized representative(s), and assent if applicable). Written informed consent for the protocol must be obtained prior to any screening procedures. If consent cannot be expressed in writing, it must be formally documented and witnessed, ideally via an independent trusted witness.
8. Willingness and ability to comply with scheduled visits, treatment plans, laboratory tests and other procedures.
9. Age  $\geq 18$  at time of consent
10. Have a performance status (PS) of  $\leq 2$  on the Eastern Cooperative Oncology (Group (ECOG) scale (*Oken et al. 1982*)
11. Ability to swallow oral medications.
12. Has adequate bone marrow and organ function as defined by the following laboratory values (as assessed by the local laboratory for eligibility):

**Adequate bone marrow function:**

absolute neutrophil count  $\geq 1,000/\text{mcL}$

Platelets (at time of surgery)  $\geq 100,000/\text{mcL}$

hemoglobin  $\geq 8.0 \text{ g/dL}$

Participants may receive erythrocyte transfusions to achieve this hemoglobin level at the discretion of the investigator.

**Adequate hepatic and renal function:**

total bilirubin  $\leq 1.5 \times \text{ULN}$ .

Participants with Gilbert's syndrome with a total bilirubin  $\leq 2.0$  times ULN and direct bilirubin within normal limits are permitted.

AST(SGOT)  $\leq 3 \times \text{institutional ULN}$

ALT(SGPT)  $\leq 3 \times \text{institutional ULN}$

Calculated or measured creatinine clearance  $\geq 45 \text{ mL/min}$

**Other Lab Values:**

Amylase or lipase	≤2 X institutional ULN
calcium or phosphorus, or calcium-phosphorus product	<55 mg  /dL 
	a. Inorganic phosphorus within normal limits b. Total corrected serum calcium within normal limits

13. Confirmed negative serum pregnancy test ( $\beta$ -hCG) before starting study treatment or participant is no longer of childbearing potential due to surgical, chemical, or natural menopause.
14. For females of reproductive potential: use of highly effective contraception for at least 1 month prior to screening and agreement to use such a method during study participation and for an additional 3 months after the end of treatment administration.
15. For males of reproductive potential: use of condoms or other methods to ensure effective contraception with partner and for an additional 1 month after the end of treatment administration. A condom is required to be used also by vasectomized men as well as during intercourse with a male partner to prevent delivery of the drug via seminal fluid.
16. Agreement to adhere to Lifestyle Considerations (see Section 5.3) throughout study duration.
17. Participants who received chemotherapy must have recovered (Common Terminology Criteria for Adverse Events [CTCAE] Grade  $\leq 1$ ) from the acute effects of chemotherapy except for residual alopecia or Grade 2 peripheral neuropathy prior to Day 1. A washout period of at least 21 days is required between last chemotherapy dose and Day 1 (provided the patient did not receive radiotherapy).
18. Participants who received radiotherapy must have completed and fully recovered from the acute effects of radiotherapy. A washout period of at least 14 days is required between end of radiotherapy and Day 1.

## 5.2 EXCLUSION CRITERIA

An individual who meets any of the following criteria will be excluded from participation in this study:

1. Have a history of liver transplant.
2. Have impairment of gastrointestinal (GI) function or GI disease that may significantly alter the absorption of oral infigratinib (e.g., ulcerative diseases, uncontrolled nausea, vomiting, diarrhea, malabsorption syndrome, small bowel resection).
3. Known active systemic bacterial infection (requiring intravenous [IV] antibiotics at time of initiating study treatment), fungal infection, or detectable viral infection (such as known human immunodeficiency virus positivity or with known active hepatitis B or C [for example, hepatitis B surface antigen positive]). Screening is not required for enrollment.
4. Have a history and/or current evidence of extensive tissue calcification including, but not limited to, the soft tissue, kidneys, intestine, myocardium, vascular system, and lung with the exception of calcified lymph nodes, minor pulmonary parenchymal calcifications, and asymptomatic coronary calcification.
5. Have current evidence of corneal or retinal disorder/keratopathy including, but not limited to, bullous/band keratopathy, inflammation or ulceration, keratoconjunctivitis confirmed by ophthalmic examination. Subjects with asymptomatic ophthalmic conditions assessed by the investigator to pose minimal risk for study participation may be enrolled in the study.
6. Have current evidence of endocrine alterations of calcium/phosphate homeostasis, e.g., parathyroid disorders, history of parathyroidectomy, tumor lysis, tumoral calcinosis etc.
7. Have had a recent ( $\leq 3$  months prior to first dose of study drug) transient ischemic attack or stroke.

A Phase 0 Study of Infigratinib in Recurrent Glioblastoma Patients  
Protocol 2020-08

8. CTCAE (v5.0) Grade  $\geq 2$  hearing loss.
9. CTCAE (v5.0) Grade  $\geq 2$  neuropathy.
10. Have clinically significant cardiac disease including any of the following:
  - a. Known congestive heart failure requiring treatment (New York Heart Association Grade  $\geq 2$ ), LVEF  $< 50\%$  or local lower limit of normal as determined by MUGA scan or echocardiogram (ECHO), or uncontrolled hypertension (refer to the European Society of Cardiology and European Society of Hypertension guidelines [[Williams et al 2018](#)]).
  - b. Presence of Common Terminology Criteria for Adverse Events (CTCAE) v5.0 Grade  $\geq 2$  ventricular arrhythmias, atrial fibrillation, bradycardia, or conduction abnormality.
  - c. Unstable angina pectoris or acute myocardial infarction  $\leq 3$  months prior to first dose of study drug.
  - d. QTcF  $> 470$  msec (males and females). Note: If the QTcF is  $> 470$  msec in the first ECG, a total of 3 ECGs separated by at least 5 minutes should be performed. If the average of these 3 consecutive results for QTcF is  $\leq 470$  msec, the participant meets eligibility in this regard.
  - e. Known history of congenital long QT syndrome.
11. Has serious and/or uncontrolled preexisting medical condition(s) that, in the judgment of the investigator, would preclude participation in this study (for example, interstitial lung disease, severe dyspnea at rest or requiring oxygen therapy, severe renal impairment [e.g. estimated creatinine clearance  $< 30\text{ml/min}$ ], history of major surgical resection involving the stomach or small bowel, or preexisting Crohn's disease or ulcerative colitis or a preexisting chronic condition resulting in baseline Grade 2 or higher diarrhea).
12. Prior therapy with any mitogen-activated protein kinase (MEK) or FGFR inhibitor. Prior therapy is defined as a therapeutic dosing, as determined by the Investigator.
13. Are currently receiving or are planning to receive during participation in this study, treatment with agents that are known strong inducers or inhibitors of CYP3A4 and medications which increase serum phosphorus and/or calcium concentration. Participants are not permitted to receive enzyme-inducing anti-epileptic drugs, including carbamazepine, phenytoin, phenobarbital, and primidone.
14. Current use of coumarin-derived anticoagulant for treatment, prophylaxis or otherwise. Therapy with heparin, low molecular weight heparin (LMWH) or fondaparinux is allowed.
15. Have any known hypersensitivity to gemcitabine, cisplatin, calcium-lowering agents, infigratinib, or their excipients.
16. Treatment with another investigational drug or other intervention within 30 days prior to enrollment or within 5 half-lives of the investigational product, whichever is longer.
17. Have consumed grapefruit, grapefruit juice, grapefruit hybrids, pomegranates, star fruits, pomelos, Seville oranges or products containing juice of these fruits within 7 days prior to first dose of study drug.
18. Have used medications known to prolong the QT interval and/or are associated with a risk of Torsades de Pointes (TdP) 7 days prior to first dose of study drug.
19. Have used amiodarone within 90 days prior to first dose of study drug.

### 5.3 LIFESTYLE CONSIDERATIONS

During the Phase 0 portion study, participants are asked to:

- No herbal or dietary supplements known as strong inhibitors or inducers of CYP3A4 are permitted.

A Phase 0 Study of Infigratinib in Recurrent Glioblastoma Patients  
Protocol 2020-08

- Refrain from consumption of red wine, grapefruit, grapefruit juice, grapefruit hybrids, pomegranates, star fruits, pomelos, Seville oranges or products containing juice of these fruits from 7 days before the start of study treatment until after the final dose during Phase 0 ([Lilja 2000](#)).
- Abstain from caffeine- or xanthine-containing products (e.g., coffee, tea, cola drinks, and chocolate) for 24 hours before Day 1 until after collection of the final pharmacokinetic (PK) and/or pharmacodynamic sample in Phase 0.
- Abstain from alcohol for 24 hours before the start of Day 1 until after collection of the final PK and/or pharmacodynamic sample in Phase 0.
- Abstain from strenuous exercise for 24 hours before each blood collection for clinical laboratory tests. Participants may participate in light recreational activities during studies (e.g., watching television, reading).

#### 5.3.1 GENERAL GUIDANCE FOR WOMEN OF CHILDBEARING POTENTIAL AND/OR USE OF CONTRACEPTIVE METHODS

Infigratinib could cause fetal harm and developmental abnormalities. Advise participants of the potential risk to the fetus and to use effective contraception while on infigratinib and for at least 3 months following the last dose. ([QED 2019](#))

- A female of childbearing potential must have a negative serum pregnancy test within 28 days of the first dose of infigratinib and agree to use a highly effective contraception method for at least 1 month prior to treatment and for 3 months following the last dose of infigratinib.
- Contraceptive methods may include an intrauterine device [IUD] or barrier method. If condoms are used as a barrier method, a spermicidal agent should be added as a double barrier protection.
- Use of condoms or other methods to ensure effective contraception with partner and for an additional 3 months after the end of treatment administration. A condom is required to be used also by vasectomized men as well as during intercourse with a male partner to prevent delivery of the drug via seminal fluid.
- Cases of pregnancy that occur during maternal exposures to infigratinib should be reported. If a patient or spouse/partner is determined to be pregnant following infigratinib initiation, she must discontinue treatment immediately. Data on fetal outcome and breast-feeding are to be collected for regulatory reporting and drug safety evaluation.

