	
Other Lab Values:
 
 
 Amylase or lipase	<math>\leq 2 \times \text{institutional ULN}</math>	
 
	Amylase or lipase	$\leq 2 \times \text{institutional ULN}$						
Amylase or lipase	$\leq 2 \times \text{institutional ULN}$								

A Phase 0 Study of Infigratinib in Recurrent Glioblastoma Patients  
Protocol 2020-08

	
calcium or phosphorus, or calcium-phosphorus product
 
<math>\leq 55 \text{ mg}^2/\text{dL}^2</math>
 
a. Inorganic phosphorus within normal limits b. Total corrected serum calcium within normal limits
 
13. Confirmed negative serum pregnancy test (<math>\beta</math>-hCG) before starting study treatment or participant is no longer of childbearing potential due to surgical, chemical, or natural menopause.
 
14. For females of reproductive potential: use of highly effective contraception for at least 1 month prior to screening and agreement to use such a method during study participation and for an additional 3 months after the end of treatment administration.
 
15. For males of reproductive potential: use of condoms or other methods to ensure effective contraception with partner and for an additional 1 month after the end of treatment administration. A condom is required to be used also by vasectomized men as well as during intercourse with a male partner to prevent delivery of the drug via seminal fluid.
 
16. Agreement to adhere to Lifestyle Considerations (see Section 5.3) throughout study duration.
 
17. Participants who received chemotherapy must have recovered (Common Terminology Criteria for Adverse Events [CTCAE] Grade <math>\leq 1</math>) from the acute effects of chemotherapy except for residual alopecia or Grade 2 peripheral neuropathy prior to Day 1. A washout period of at least 21 days is required between last chemotherapy dose and Day 1 (provided the patient did not receive radiotherapy).
 
18. Participants who received radiotherapy must have completed and fully recovered from the acute effects of radiotherapy. A washout period of at least 14 days is required between end of radiotherapy and Day 1.

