### 8.3.9 REPORTING OF PREGNANCY

Pregnancy is not considered an adverse event unless it is a spontaneous abortion. Each pregnancy occurring while the participant is on study treatment must be reported to IBTC-CC within 24 hours of learning of its occurrence. Participants who become pregnant during the trial must be withdrawn. The pregnancy will be followed up from the estimated date of delivery plus 3 months to determine outcome, including spontaneous or voluntary termination, details of the birth, and the presence or absence of any birth defects, congenital abnormalities, or maternal and/or newborn complications.

Women of childbearing potential should be advised to use highly effective contraception methods while they are receiving study treatment and up to 3 months after treatment has been stopped.

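### Men are told to continue contraception for 1 month after treatment in inclusion criterion 15 but for 3 months in Section 5.3.1, and nothing says which applies

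*Combined protocol and SAP*

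**What the plan says.** Criterion 15 appears twice. The Synopsis reads "For males of reproductive potential: use of condoms or other methods to ensure effective contraception with partner and for an additional 1 month", counted from when dosing stops. Section 5.1 gives the same period: "use of condoms or other methods to ensure effective contraception with partner and for an additional 1 month after the end of treatment administration".

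Section 5.3.1 repeats the rule in its third bullet with a different figure: "Use of condoms or other methods to ensure effective contraception with partner and for an additional 3 months after the end of treatment administration". The bullet goes on: "A condom is required to be used also by vasectomized men as well as during intercourse with a male partner". Criterion 15 carries the same follow-on sentence in both of its locations. The opening paragraph of 5.3.1 warns that the drug may harm a fetus and tells sites to advise participants, without distinguishing by sex, "to use effective contraception while on infigratinib and for at least 3 months following the last dose".

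Two other places bear on the question. Criterion 16 requires "Agreement to adhere to Lifestyle Considerations (see Section 5.3) throughout study duration". Section 8.3.9 addresses women only, again counting from when dosing stops: "Women of childbearing potential should be advised to use highly effective contraception methods while they are receiving study treatment and up to 3 months".

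**The concern.** The rule for men is a safety instruction that sites apply directly when they check eligibility and counsel participants. Its stated purpose is to prevent the drug from reaching a partner through seminal fluid. If two sections give different durations, sites can give different advice (up to three sites are planned), and each could point to protocol text in support. The risk falls on partners and on any pregnancy conceived in the interval between the two figures. The trial's statistical results are not at stake.

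**Working it through.** There is no statistical figure to reproduce, so the check sets the current texts side by side.

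| Location | Who it addresses | Period after treatment |
|---|---|---|
| Synopsis 1.1, criterion 15 | men | 1 month |
| Section 5.1, criterion 15 | men | 1 month |
| Section 5.3.1, third bullet | men (see step 1) | 3 months |
| Section 5.3.1, opening paragraph | participants in general | at least 3 months |
| Synopsis 1.1 and Section 5.1, criterion 14 | women | 3 months |
| Section 5.3.1, first bullet | women | 3 months |
| Section 8.3.9 | women | up to 3 months |

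1. **Is the third bullet of 5.3.1 the male rule?** Yes. The section heading names women first but also covers contraceptive methods generally. The bullet omits the introductory reference to males, but its wording otherwise matches criterion 15, and the next sentence concerns vasectomized men and seminal fluid.

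2. **Size of the discrepancy.** 3 months − 1 month = 2 months. The male rule is printed twice at 1 month and once at 3 months.

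3. **Does another section settle it?** Section 8.3.9 does not, because it is confined to women. Criterion 16 points to Section 5.3 but limits the commitment to the duration of the study and does not mention the period after treatment. The list that opens Section 5.3 is introduced as applying to the Phase 0 portion. The End of Study Definition counts a participant as complete once Phase 0 and the follow-up phone call are done. The Schedule of Activities places that call about 30 days after the last dose, although survival follow-up continues. On that reading, criterion 16 might not reach 3 months after treatment.

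4. **Is this a leftover from an amendment?** The amendment history in Section 10.3 does not mention contraception, and all three statements of the male rule are in the current text.

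5. **How many people?** Sections 1.1 and 4.1 plan for up to 20 participants, and only men of reproductive potential among them are affected. Their number is not given. Section 7.2 allows dosed participants who leave the study to be replaced, so the number of people dosed could exceed 20, depending on how the limit is applied.

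**The case against.** The best counter-argument is that the criteria are cumulative. Section 5.1 requires a participant to meet all of them, so criteria 15 and 16 apply together. Criterion 16 brings in Section 5.3, of which 5.3.1 is a part. Three months satisfies both and 1 month does not, so no precedence clause is needed. The general advice at the start of 5.3.1, which cites the Investigator's Brochure, points the same way. Participants also take their instructions from the consent form, which is not available here and may already say 3 months.

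Part of this stands. Three months is the better reading of the protocol as a whole, and following it breaches nothing. But the reader has to infer it, for the reasons in step 3, while criterion 15 states the shorter period expressly as the condition for men. Early release is a risk only where a site works from criterion 15 alone, and nothing in the documents shows how likely that is. It is also fair to say that a shorter period for men could be justified. In that case the third bullet of 5.3.1 is the text in error, so one of the two needs correcting either way.

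**Conclusion.** The inconsistency is real and present in the current text: 1 month in criterion 15 (twice) against 3 months in Section 5.3.1, a gap of 2 months for the same male requirement. The female figure is 3 months wherever a number is given, although 5.3.1 opens with a minimum and 8.3.9 words it as a maximum.

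The documents do not show which duration is right for men, because the Investigator's Brochure cited in 5.3.1 is not available here. Preferring 3 months is therefore the cautious choice, not an established correction. The point deserves correction because it is an operative fetal-safety instruction. It has no bearing on any endpoint, analysis population, sample size or estimate.

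**What to change.** Change 1 month to 3 months in criterion 15 in both the Synopsis (1.1) and Section 5.1, and confirm that the consent form states the same period. If the sponsor's safety source supports 1 month for men, change the third bullet of Section 5.3.1 to 1 month instead and limit the general advice in its opening paragraph to women.

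The preferred change is one number in two places plus a consent-form check. Its only burden is up to 2 further months of contraception for men who would otherwise have been instructed under criterion 15.
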